6. STUDY INTERVENTION

A ‘study intervention’ is defined as a set of investigational or marketed product(s) or placebo intended to be administered to a participant during the study.

Refer to the Study Procedures Manual (SPM) for additional details.

6.1. Study intervention(s) administered

Dose preparation is to be performed by an unblinded member of the site staff. For study vaccines adjuvanted with AS03, thorough mixing of the antigen and adjuvant components is required. Placebo does not require mixing. Detailed instructions for vaccine and placebo preparation will be provided separately in the SPM.

All vials of vaccine/product provided in this study are intended for single use only.

All used vials will be retained for monitoring and reconciliation purposes.

All doses are administered intramuscularly into the deltoid region of the non-dominant arm. All study vaccines will be administered by an unblinded member of the site staff who may also participate in dose preparation, but who is barred from participation in any other study functions and may not contribute any observations.

The needle for any intramuscular injection should be long enough to reach the muscle mass and prevent vaccine from seeping into subcutaneous tissue, but not so long as to involve underlying nerves and blood vessels or bone. Vaccinators should be familiar with the anatomy of the area into which they are injecting vaccine.

A summary of the study interventions can be found in [Table 6](#). The schedule of study intervention administration can be found in [Section 4](#).

Table 6 Study interventions administered

Study Intervention Name:	1.9 µg HA + AS03B **		1.9 µg HA + AS03A *		3.75 µg HA + AS03B **		3.75 µg HA + AS03A *							
Vaccine/Product name:	FLU-Q-PAN H7N9 (1.9)		AS03B		FLU-Q-PAN H7N9 (1.9)		AS03A							
Presentation:	Suspension for suspension for injection in vial	Emulsion for suspension for injection in vial	Suspension for suspension for injection in vial	Emulsion for suspension for injection in vial	Suspension for suspension for injection in vial	Emulsion for suspension for injection in vial	Suspension for suspension for injection in vial	Emulsion for suspension for injection in vial						
Vaccine/product formulation:	A/Hong Kong/125/2017 - like (H7N9) (1.9 µg HA); Water for injections q.s. 0.125 mL	AS03B: DL- α -tocopherol and squalene in an o/w emulsion (5.93 mg DL- α -tocopherol); Water for injections q.s. 0.125 mL	A/Hong Kong/125/2017 - like (H7N9) (1.9 µg HA); Water for injections q.s. 0.125 mL	AS03A: DL- α -tocopherol and squalene in an o/w emulsion (11.86 mg DL- α -tocopherol); Water for injections q.s. 0.25 mL	A/Hong Kong/125/2017 - like (H7N9) (3.75 µg HA); Water for injections q.s. 0.125 mL	AS03B: DL- α -tocopherol and squalene in an o/w emulsion (5.93 mg DL- α -tocopherol); Water for injections q.s. 0.125 mL	A/Hong Kong/125/2017 - like (H7N9) (3.75 µg HA); Water for injections q.s. 0.25 mL	AS03A: DL- α -tocopherol and squalene in an o/w emulsion (11.86 mg DL- α -tocopherol); Water for injections q.s. 0.25 mL						
Volume to be administered:	0.25 milliliter(s)		0.375 milliliter(s)		0.25 milliliter(s)		0.5 milliliter(s)							
Number of doses to be administered:	2		2		2		2							
Route of Administration:	Intramuscular use													
Administration site:														
Location	Deltoid													
Directionality	Not applicable													
Laterality****	Non-dominant													
Packaging and Labelling:	Refer to the Standard Procedures Manual for more details													
Manufacturer:	GSK Biologicals SA													
Type of contact/ Time points:	Visit 1 (Day 1), Visit 2 (Day 22)													

CONFIDENTIAL

209671 (FLU Q-PAN H7N9=AS03-002)
Protocol Amendment 2 Final

Study Intervention Name:	7.5 µg HA + AS03B **		7.5 µg HA + AS03A *		Placebo		
Vaccine/Product name:	FLU-Q-PAN H7N9 (7.5)	AS03B	FLU-Q-PAN H7N9 (7.5)	AS03A	Formulation buffer S9b ***		
Presentation:	Suspension for suspension for injection in vial	Emulsion for suspension for injection in vial	Suspension for suspension for injection in vial	Emulsion for suspension for injection in vial	Solution for injection in vial		
Vaccine/product formulation:	A/Hong Kong/125/2017-like (H7N9) (7.5 µg HA); Water for injections q.s. 0.25 mL	AS03B: DL- α -tocopherol and squalene in an o/w emulsion (5.93 mg DL- α -tocopherol); Water for injections q.s. 0.125 mL	A/Hong Kong/125/2017-like (H7N9) (7.5 µg HA); Water for injections q.s. 0.25 mL	AS03A: DL- α -tocopherol and squalene in an o/w emulsion (11.86 mg DL- α -tocopherol); Water for injections q.s. 0.25 mL	Sodium Chloride (3.85 mg); Potassium Chloride (100 µg); Magnesium Chloride (50 µg); Disodium Hydrogen Phosphate (1.3 mg); Potassium Dihydrogen Phosphate (186 µg); Water for injections q.s. 0.5 mL		
Volume to be administered:	0.375 milliliter(s)		0.5 milliliter(s)		0.5 milliliter(s)		
Number of doses to be administered:	2		2		2		
Route of Administration:	Intramuscular use						
Administration site:							
Location	Deltoid						
Directionality	Not applicable						
Laterality****	Non-dominant						
Packaging and Labelling:	Refer to the Standard Procedures Manual for more details						
Manufacturer:	GSK Biologicals SA						
Type of contact/ Time points:	Visit 1 (Day 1), Visit 2 (Day 22)						

* The AS03A doses will be prepared using adjuvant vialled at a concentration of 47.44 mg/mL tocopherol. The final AS03A doses will contain 11.86 mg tocopherol.

** The AS03B doses will be prepared as half a dilution of AS03A (with AS03A vialled at concentration of 47.44 mg/mL).

*** Placebo: formulation buffer S9b is a phosphate buffered saline.

**** The non-dominant arm is the preferred arm of injection. In case it is not possible to administer the vaccine in the non-dominant arm, an injection in the dominant arm may be performed.

o/w: oil/water

q.s.: "Quantity sufficient" stands for the Latin term "quantum satis" which means "as much as necessary" i.e. adding enough of a constituent to achieve a specific final volume or total weight. QS is a placeholder for an amount or volume which has to be "adjusted" by the given circumstances in a particular preparation [EMA]

The participants must be observed closely for at least 30 minutes after the administration of the vaccine/product. Appropriate medical treatment must be readily available during the observation period in case of anaphylaxis and/or syncope.

6.2. Preparation/Handling/Storage/Accountability

The study vaccine/product must be stored in a safe, locked place at the temperature specified on the vaccine/product label. The storage temperature should be continuously monitored with calibrated (if not validated) temperature monitoring device(s) and recorded. Only authorized study personnel should be allowed access to the study vaccine/product. Storage conditions will be assessed by a sponsor study contact during pre-study activities. Refer to the section on Study Supplies in the SPM for more details on storage and handling of the study vaccine/product.

6.3. Measures to minimize bias: randomization and blinding

6.3.1. Participant identification

Participant identification numbers will be assigned sequentially to the participants who have consented to participate in the study, according to the range of participant identification numbers allocated to each study center.

6.3.2. Randomization to study intervention

The randomization list used to number the supplies will be based on a blocking scheme using a 1:1:1:1:1:1 ratio (approximately 120 participants in each study group).

The intervention numbers will be allocated by component.

To allow GSK to take advantage of greater rates of recruitment than anticipated at individual centers in this multi-center study and to reduce the overall study recruitment period, an over-randomization of supplies of at least 5% will be prepared.

6.3.3. Intervention allocation to the participant

The enrollment will be performed to evenly distribute participants across the 2 age groups (18-64 years, \geq 65 years) (i.e. of the 120 participants in each study group, 60 participants will be aged 18 to 64 years and 60 participants will be aged \geq 65 years). Within the 18-64 years age group, the enrollment is further stratified into 18-49 years and 50-64 years to allow an even distribution of participants in terms of intervention allocation.

Central randomization will be performed using PPD Interactive Response Technology (IRT).

Allocation of the participant to a study group at the investigator site will be performed using the PPD IRT.

The IRT will determine the study group and will provide the intervention number to be used for the first vaccination. The intervention number(s) to be used for subsequent dose administration(s) will be provided by the same IRT.

The number of each administered intervention kit must be recorded in the eCRF on the Vaccine Administration form/screen.

Refer to the SPM for additional information relative to the intervention number allocation.

6.3.4. Allocation of participants to assay subsets

Vaccine-homologous microneutralization (MN) will be evaluated in a subset of approximately 420 participants (60 per group). A selection consistent of approximately 50% of participants per H7N9 vaccine group, and approximately 50% of participants from the placebo group will be generated.

PPD will select the first 30 participants per treatment group in the ≥ 65 age group and then the first 15 participants in 18 to 49 years and 50 to 64 years age groups. If there are not 15 participants for the 18 to 49 or 50 to 64 years age groups, PPD will select whichever has the smaller number fully and then have a total of 30 for the total among these 2 age groups per treatment group.

All samples will be collected first, then selected for the subset. PPD will supply the list of selected participants to Q² Solutions.

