Blood sample collection done at V3 outside of the interval between V2 and V3 of 14 - 32 calendar Days								X				X	
Blood sample collection at V3 done outside of the interval between 38 - 46 Study Days						X				X			
Subjects MN1 and MN2, who were randomized to MN set but were not included										X	X	X	X
Temperature deviations from range defined in protocol and/or SPM for vaccine stored in fridge (0-8C; site level) at V1						X	X	X	X	X	X	X	X

* Subject elimination from FAS 1 or FAS 2 must only take place in cases where blood sample results are not available for any reason above described

** Elimination will be based on case-by-case bases

Enr = Enrolled set; Exp = Exposed set; Rand = Randomized set; FAS = Full Analysis Set; PPS = Per Protocol Set; mPPS = modified Per Protocol Set; MNPPS = Microneutralization per protocol set; MNmPPS = Microneutralization modified per protocol set.

X = Exclusion from the study population set

6 Demographics and Baseline Characteristics

Demographics and baseline characteristics will be summarized for the Exposed Set, Enrolled Set, PPS1, PPS 2, mPPS1, mPPS2, presented by study group, age group, and overall. Participant demographic and baseline characteristics will also be presented in a listing for the Enrolled Set.

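### The MN subset is taken in enrolment order although all sera are collected before selection; a seeded stratified draw of the same size would remove a possible enrolment-order bias

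*Protocol*

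**What the plan says.** Protocol 6.3.4 sets the size and the rule together. On size: "Vaccine-homologous microneutralization (MN) will be evaluated in a subset of approximately 420 participants (60 per group"), described as "A selection consistent of approximately 50% of participants per H7N9 vaccine group" and about the same share of placebo. On the rule for the older stratum: "PPD will select the first 30 participants per treatment group in the ≥ 65 age group". Each of the two younger strata contributes its first 15 per arm by the same principle. If a younger stratum has fewer than 15, "PPD will select whichever has the smaller number fully and then have a total of 30" across the two younger strata. On timing: "All samples will be collected first, then selected for the subset".

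No random draw is described. Protocol Table 16 and SAP 4.6.7 define the MN Set as members of the Randomized Set who were selected, without naming a mechanism. SAP 5.2, Table 9, has an exclusion row for participants "who were randomized to MN set but were not included", which is not what Protocol 6.3.4 does.

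The documents do not define 'first' (by consent, randomization or vaccination; study-wide or by centre). SAP Section 6 plans demographic summaries for the Enrolled and Exposed Sets, PPS1, PPS2, mPPS1 and mPPS2, but not for the MN Set. No comparison of subset with non-subset participants is planned.

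**The concern.** MN results are reported as estimates for each formulation: GMT, seropositivity and vaccine response rate by study group and age group (SAP 8.2, 8.4, 8.4.1). They will be read as describing the arm. A consecutive sample does that only if response and study conduct are stable over enrolment.

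The documents give some reason to doubt stability. Protocol 6.3.2 provides for centres that recruit faster than expected, which early ranks could over-represent. Protocol 9.4.5.2 and SAP 9.2 foresee procedures modified by COVID-19. The rationale for Amendment 2 is more out-of-window visits than anticipated, and the MN per-protocol sets inherit those exclusions. Participant numbers run sequentially within ranges given to each centre (Protocol 6.3.1), so a programmer who read 'first' as lowest number would concentrate the subset in a few centres.

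Because every serum is in hand at selection, the text shows no logistical need for the rule.

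**Working it through.** **1. Reproduce the plan's figures.** From the rule in Protocol 6.3.4: 30 + 15 + 15 = 60 per group; 7 × 60 = 420; 420/840 = 50%. All three agree with the stated size.

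**2. What the rule takes.** Protocol 6.3.3 plans that in each arm "60 participants will be aged 18 to 64 years and 60 participants will be aged" 65 or over. In the older stratum the rule therefore takes ranks 1 to 30 of 60, with mean rank 15.5 against 30.5 for a random draw. It takes 0 from the second half. A simple random 30 of 60 would take 15 on average (central 95% range 11 to 19, hypergeometric), and would miss the second half entirely with probability 1/C(60,30) = 8.5 × 10⁻¹⁸.

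The documents do not fix the sizes of the 18-49 and 50-64 strata. If each is about 30 per arm, the first 15 is again the first half.

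**3. Size of the possible error.** Let d be the difference in true mean log10 titre between the early and late halves. The whole-group mean is the average of the two halves, so the subset is off by d − d/2 = d/2 and the GMT by a factor of 10^(d/2). For a response rate the same halving applies: an early-late difference of 5, 10 or 20 points gives an error of 2.5, 5 or 10 points. A random draw has expected error 0.

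**4. Effect on the confidence interval.** The documents give neither the SD of log10 MN titre nor any drift. Assume SD = 0.6 and d = 0.1 to 0.3. Then SE = 0.6/√n, b = (d/2)/SE, and coverage = Φ(1.96 − b) − Φ(−1.96 − b).

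- n = 60 (arm, ages pooled): SE = 0.077
- n = 30 (65 or over, or 18-64 combined): SE = 0.110

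| d (log10) | GMT factor | Coverage, n=60 | Coverage, n=30 |
|---|---|---|---|
| 0.1 | 1.12 | 90% | 93% |
| 0.2 | 1.26 | 75% | 85% |
| 0.3 | 1.41 | 51% | 72% |

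The GMT factor does not depend on n. Coverage is better at n=30 only because the interval is wider. The age-group column is the more relevant one, since the SAP reports MN by age group.

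**5. Precision after the fix.** The numbers per stratum do not change, so nominal precision does not change. For example, 24 responders of 30 gives a Clopper-Pearson 95% CI of 61.4% to 92.3% under either rule.

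**The case against.** The strongest reply is that the harm is hypothetical and the stakes are low.

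- **Drift is not documented.** The protocol and SAP give no site activation dates, accrual pattern or change in response over time. d = 0.3 would mean a two-fold titre difference (10^0.3 ≈ 2) between early and late participants on the same formulation. Part of any drift in visit timing is removed by the window exclusions in SAP Table 9, and COVID-19 infection or vaccination may lead to per-protocol exclusion. This stands: the table in the working is an illustration, not an estimate.
- **The rule is the same in every arm.** Within age strata of a randomized trial, between-arm MN comparisons are largely protected. This stands.
- **MN is secondary and descriptive.** It has no hypothesis, and the primary HI analysis does not use the subset. This stands.
- **A redraw needs a protocol change.** Protocol 10.1.1 requires ethics approval before a design change is implemented. This stands as a cost of procedure, not of assays or samples.
- **Table 9 is one loose row label.** It is an editorial slip when set against the two set definitions. It still has to be reconciled.

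A reader might go further and infer that MN results describe only a small initial cohort and cannot be set beside the HI results. The documents do not support that. The subset is about half of each arm, and a younger stratum with fewer than 15 is taken in full and so spans all enrolment. HI is planned for all 840 participants (Protocol Table 9), including every MN participant, and SAP Section 8 lists both titres by participant. MN and HI can therefore be compared in the same people.

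**Conclusion.** The point holds as an avoidable weakness in sampling, together with a mismatch between the documents. The selection is consecutive, no reason is given, all sera are available when it is made, and SAP Table 9 describes a mechanism that the protocol does not use.

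The consequence is conditional. Per-arm MN estimates could differ from whole-arm values by half of any early-late difference; the log10 figures above rest on an assumed SD of 0.6 and assumed d. The d/2 result is exact for the stratum aged 65 or over at planned enrolment, and holds in a younger stratum only if it enrols about 30 per arm. Between-arm MN contrasts are largely protected and the primary HI conclusions are unaffected. The change is worth making because it removes the question without more assays, not because bias has been shown.

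**What to change.** **If the subset has not been selected.** Replace the consecutive rule in Protocol 6.3.4 with a seeded random draw, stratified by arm and age stratum: 30 aged 65 or over, 15 aged 18-49 and 15 aged 50-64 per arm, keeping the present top-up rule. Draw from the Randomized Set, which is already the frame for the MN Set, so that selection is not conditioned on later attendance. The unblinded statistician should fix the list before any HI or MN result is seen. SAP Table 9 would then be correct as worded. The cost is one sentence in the protocol, one short program and whatever approval the amendment needs; the numbers of samples and assays do not change. The present rule also works per arm and so already needs the treatment codes.

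**If selection has already been made.** State how 'first' was defined and applied, correct the Table 9 wording, and add a comparison of subset with non-subset participants within arm and age stratum on centre, baseline characteristics and HI titres. HI is measured in everyone, so this needs no new assays, and it would show whether an enrolment-order difference is visible in the HI response.

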6.3.5. Blinding and unblinding

Data will be collected in an observer-blind manner. To do so, vaccine/product will be prepared and administered by qualified study personnel who will not participate in data collection, evaluation, review or the entry of any study endpoint (i.e. reactogenicity, safety, efficacy).

The laboratory in charge of the sample testing will be blinded to the intervention assignment. Codes will be used to link the participant and study (without any link to the intervention attributed to the participant) to each sample.

Investigators will remain blinded to each participant's assigned study intervention throughout the course of the study. In order to maintain this blind, an otherwise uninvolved third party will be responsible for the reconstitution and dispensation of all study intervention and will endeavor to ensure that there are no differences in time taken to dispense following randomization.

This third party will instruct the participant to avoid discussing the dosing site or visual appearance of the study intervention with the investigator. Unblinded monitors, and in the event of a Quality Assurance audit, the auditor(s) will be allowed access to unblinded study intervention records at the site(s) to verify that the randomization/dispensing has been done accurately.

The IRT will be programmed with blind-breaking instructions. In case of an emergency, the investigator has the sole responsibility for determining if unblinding of a participant's intervention assignment is warranted. Please refer to the Section [6.3.5.1](#) for details regarding emergency unblinding.

A statistical team will be unblinded for the interim analysis outlined in Section [9.5](#).

6.3.5.1. Emergency unblinding

Unblinding a participant's individual intervention number should occur ONLY in case of a medical emergency when knowledge of the intervention is essential for the clinical management or welfare of the participant.

The emergency unblinding process enables the investigator to have unrestricted, immediate and direct access to the participant's individual study intervention via IRT.

The IRT will be programmed with blind-breaking instructions. In case of an emergency, the investigator has the sole responsibility for determining if unblinding of a participant's intervention assignment is warranted. Participant safety must always be the first consideration in making such a determination. If the investigator decides that unblinding is warranted, the investigator should make every effort to contact PPD prior to unblinding a participant's intervention assignment unless this could delay emergency treatment of the participant. If a participant's intervention assignment is unblinded, PPD must be notified within 24 hours after breaking the blind. The date and reason that the blind was broken must be recorded in the source documentation and eCRF, as applicable. Refer to Section [8.3.3.1](#) for emergency contact information.

6.3.5.2. Unblinding prior to regulatory reporting of SAEs

A participant may continue in the study if that participant's intervention assignment is unblinded provided that there are no safety concerns for the participant per the investigator's judgement.

GSK policy (which incorporates International Council on Harmonisation [ICH] E2A guidance, the EU Clinical Trial Directive and US Federal Regulations) is to unblind the report of any unexpected Serious Adverse Event (SAE) and which is attributable/suspected to be attributable to the study vaccine/product, prior to regulatory reporting. Vaccines Clinical Safety and Pharmacovigilance (VCSP) is responsible for unblinding the intervention assignment in accordance with the specified timeframes for expedited reporting of SAEs (refer to the Section [10.3.10.1](#)).

In addition, GSK VCSP staff may unblind the intervention assignment for any participant with a Suspected Unexpected Serious Adverse Reaction (SUSAR) or an SAE that is fatal or life threatening. If the SAE requires an expedited regulatory report be sent to 1 or more regulatory agencies, a copy of the report, identifying the participant's intervention assignment, may be sent to investigators in accordance with local regulations and/or GSK policy.

6.4. Study intervention compliance

All doses will be administered at the site under medical supervision. Each dose will be administered by an unblinded member of the site staff who could also participate in dose preparation but who is barred from participation in any other study functions and cannot contribute to any observations. The date and time of each dose administered in the clinic will be recorded in the source documents and in the eCRF. The dose of study intervention and study participant identification will be confirmed at the time of dosing by a member of the study site staff other than the person administering the study intervention. The number of each administered intervention kit must be recorded in the eCRF on the Vaccine Administration form/screen.

